3.2.5 Development of cognitive decline

The MoCA will be performed at baseline and day 100. Cognitive decline will be defined as a 2 point or greater decline from baseline on the total score at the day 100 re-evaluation. Cognitive decline will be assessed in all patients in subgroups who do and who do not have relapse of their malignancy prior to day 100.

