In HCT, most studies of cognitive function have reported on younger allogeneic HCT recipients.³⁸ The Houston series of adults 60 years and older utilizing a GA described a 16% prevalence of mild cognitive impairment to transplant.²⁵ The etiology and consequences of HCT in older adults manifesting cognitive difficulties are not established. However, outcomes of non-transplant intensive chemotherapy for hematologic malignancy is inferior in older subjects found to have cognitive impairment by screening tools compared to those with normal cognition.^{39, 40} This suggests mild cognitive impairment should be incorporated in models to better delineate HCT risks in older adults.

Cognitive changes after transplant are of considerable interest. Joint recommendations from the CIBMTR and EBMT highlighted the need for larger prospective studies.³⁸ The review summarized the post-transplant changes as perhaps some early cognitive changes in the first few months that often return to baseline with considerable individual variation. A meta-analysis of autologous and allogeneic HCT indicated from studies employing formal neuropsychological testing showed no major cognitive changes after transplant.⁴¹ However, the median age of participants across all studies was 42 years. We advocate a simpler approach of repeating the MoCA at day 100. Although data and trajectories in HCT are lacking, studies in the stroke literature have proposed the minimally important difference for the MoCA was 2.^{42 43}

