5.8 Analysis of Secondary Endpoints

Three risk groups will be formed, based on the tertiles of the CHARM risk score. We will provide univariate summaries of each of the secondary outcomes by CHARM score risk group for each endpoint. We will then compare the risk groups multivariate models developed for each outcome separately as detailed below. All the demographic and baseline characteristics described in section 5.6 above will be considered via stepwise variable selection for inclusion in the model. Assuming an overall type I error of 10%, a significance level of 1% will be used for all secondary analyses based on Bonferroni adjustment since we will be considering 10 endpoints between section 5.8.1 and 5.8.9. A sensitivity analyses will also be done base on the CHARM score as a quantitative measure rather than tertile groups.

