5.8.5 Development of Cognitive Decline

The frequency of cognitive decline will be described by creating a change score from baseline to the day 100 evaluation with a score 2 or less from baseline at day 100 reflecting decline. The effect of CHARM risk groups on cognitive decline will be modeled using logistic regression model.

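### Cognition is tested against CHARM only as a yes/no fall of 2 or more MoCA points; a baseline-adjusted model of the score would use the data better

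*Protocol*

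**What the plan says.** - **Endpoint.** Protocol 3.2.5: "Cognitive decline will be defined as a 2 point or greater decline from baseline on the total score at the day 100 re-evaluation".
- **Analysis.** Protocol 5.8.5 forms a change score, classifies it ("with a score 2 or less from baseline at day 100 reflecting decline"), and then: "The effect of CHARM risk groups on cognitive decline will be modeled using logistic regression model". No model of the score is stated.
- **Reason for the cut.** Protocol 1.6.3: "studies in the stroke literature have proposed the minimally important difference for the MoCA was 2". The same sentence opens with a caveat: "Although data and trajectories in HCT are lacking".
- **Groups and level.** Protocol 5.8: "Three risk groups will be formed, based on the tertiles of the CHARM risk score", and "a significance level of 1% will be used for all secondary analyses based on Bonferroni adjustment".
- **Sensitivity analysis.** Protocol 5.8 plans one that is "base on the CHARM score as a quantitative measure rather than tertile groups". It changes the predictor and leaves the outcome binary.
- **Administration.** Appendix 3.3 (6.3.3 and 6.3.3.1) allows a telephone MoCA with a maximum of 22 points, against 30 in person or by video.

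**The concern.** The MoCA total is collected at baseline and day 100 and then reduced to two categories before CHARM is tested. A fall of 2 points and a fall of 8 count the same, and a fall of 1 counts as none. With a single retest, some subjects whose cognition has not changed will cross the cut through measurement variation. If that misclassification is unrelated to CHARM, it pulls the odds ratio towards 1. At the 1% level, a null result could reflect the dichotomy and not the absence of an association. Disability (5.8.3) and the PROMIS scales (5.8.6) each have a mean-score analysis by CHARM group; cognition has none.

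**Working it through.** **Inputs from the protocol.** Evaluable N is 880 (5.5): 12 × 16 / 0.22 = 872.7, consistent with the stated 880. Alpha is 0.10 / 10 = 0.01 (5.8), taken here as two-sided. Survival to day 100 by age band is in Table 5.9.2. The protocol states no power, decline rate, SD or retest reliability for the MoCA, so it has no figure of its own to reproduce for this endpoint.

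**Assumed inputs.** The SD of MoCA change, the mean change, and the CHARM difference are all assumed. Change is treated as normal and rounded to whole points. Ceiling and practice effects are ignored.

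**Subjects available.** Pooled 100-day survival = (1617×88 + 1816×87 + 704×84 + 81×81) / 4218 = 86.8%. This gives about 764 of 880, or about 254 per tertile. If 80-90% of survivors are tested (assumed), that is about 204-229 per tertile, treating the tertiles as equal at day 100.

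**1. Stable subjects flagged.** On whole-number scores a fall of 2 or more is a latent change below −1.5, so with no true change the probability is Φ(−1.5/SD).

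| SD of change | Flagged, whole-point scores | Flagged without rounding, Φ(−2/SD) |
|---|---|---|
| 1.0 | 6.7% | 2.3% |
| 1.5 | 15.9% | 9.1% |
| 2.0 | 22.7% | 15.9% |
| 2.5 | 27.4% | 21.2% |
| 3.0 | 30.9% | 25.2% |
| 4.0 | 35.4% | 30.9% |

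**2. Information kept by the cut.** Relative efficiency for a small shift is φ(z)² / [p(1−p)], where p is the decline rate and z its normal quantile.

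| Decline rate p | Efficiency | Loss |
|---|---|---|
| 16% | 0.44 | 56% |
| 20% | 0.49 | 51% |
| 25% | 0.54 | 46% |
| 30% | 0.58 | 42% |
| 50% | 0.64 | 36% |

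The smallest possible loss, at p = 50%, is about 36%.

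**3. Illustrative power.** Outer tertiles, 200 each, two-sided 1% (critical value 2.576), reference tertile with no mean change, difference 0.7 points, SD 2.0.
- Score: SE = 2.0 × √(2/200) = 0.20; z = 0.7/0.20 = 3.50; power = Φ(3.50 − 2.576) = 82%.
- Cut: p₀ = Φ(−1.5/2) = 0.227 and p₁ = Φ(−0.8/2) = 0.345; log odds ratio 0.584, SE 0.225, z = 2.60; power = Φ(2.60 − 2.576) = 51%.

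Other cases by the same formulas, 200 per group:

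| SD | Difference | Score | Cut |
|---|---|---|---|
| 1.5 | 0.7 | 98% | 75% |
| 2.5 | 0.7 | 59% | 33% |
| 2.0 | 1.0 | 99% | 87% |
| 2.5 | 1.0 | 92% | 69% |

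With 254 per group, SD 2.0 and difference 0.7, the figures are 91% against 64%.

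**4. Telephone version.** Dropping the visuospatial/executive block (5 points) and naming (3 points) leaves 30 − 8 = 22. If a 30-point baseline were compared directly with a 22-point day-100 total, anyone with a baseline of 24 or more would be counted as falling by at least 2, whatever their cognition. The protocol states no rule for this comparison. It affects the cut and a score model alike.

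**The case against.** The best case for the plan has several parts.

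- **The cut is prespecified and reasoned.** It follows a cited minimally important difference, and the stated objective is decline at day 100, which is naturally a responder question. This stands. A mean comparison answers a somewhat different question, so the proportion should be kept.
- **A reader might infer that 16-27% of stable subjects will be mislabelled.** The documents do not support that as a fact, because they give no retest SD. The range is conditional on SD 1.5-2.5 and whole-point scoring; without rounding it is 9-21%.
- **A reader might infer that half the information is always lost.** That holds only for decline rates near 20%. If subjects fall by 0.5-1 point on average, efficiency is 0.54-0.63 for SD 1.5-2.5, a loss of 37-46%.
- **A reader might infer that a real association will probably be missed.** The documents do not support this. The 0.7-point effect is unsourced and about a third of the 2-point difference that the protocol calls important. At 1.0 point the cut already has 87% power (SD 2.0) or 69% (SD 2.5), and at 1.5 points at least about 98%. The quantitative-CHARM sensitivity analysis would also recover some power, though its outcome stays binary.
- **Cognition is not a lone exception.** Frailty (3.2.2, 5.8.2) also thresholds a score and has no mean-score model. Disability and PROMIS have three follow-up assessments, while the MoCA has one. The contrast in the protocol is therefore weaker than it first looks.
- **The analysis plan, not shown, might add a score model.** It might, but the protocol already names the test for this endpoint, and the objection is to that stated choice.

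**Conclusion.** The point holds as an efficiency weakness in one of ten secondary endpoints. It is not an error in the definition and does not touch the primary endpoint. What follows without knowing the SD is that, under a normal model, testing only the dichotomy costs at least about 36% of the information. The proportion of stable subjects flagged (about 16-27% for SD 1.5-2.5, about 7-35% for SD 1-4) and the power figures (82% against 51% in the illustrated case) rest on assumed inputs and should be read as such. Misclassification unrelated to CHARM would weaken an observed association, not produce a false one. The minimally important difference supports reporting a 2-point fall; it does not by itself show that such a fall on one retest exceeds measurement error, or that the rest of the score should go unused in the test.

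**What to change.** - **Test.** In 5.8.5, make the CHARM comparison a linear model of the day-100 MoCA score with baseline MoCA as a covariate and robust standard errors, at the 1% level. Robust errors address the variance only; the ceiling at 30 still limits how the mean difference can be read, and the report should say so.
- **Companion.** Keep the proportion with a fall of 2 or more points, by CHARM group, as the clinical result. Align the classification wording in 5.8.5 with 3.2.5, since a score of 2 or less from baseline does not clearly say a fall of at least 2.
- **Telephone MoCA.** For subjects tested by telephone, compare baseline and day 100 on the items common to both administrations (the 22-point subscore), or analyse these subjects separately. Apply the same rule to the 2-point cut.
- **Cost.** A wording change and one extra model, with no new assessments. The common-item comparison needs item or section scores to have been recorded. The main downside is that the tested effect is in MoCA points and not a proportion of decliners, which is why the proportion stays alongside it.

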3.2.6 Health Related Quality of Life

PROMIS Global Health Physical Function, Anxiety and Depression will be measured at baseline and then at day 100, day 180, and day 365.

3.2.7 GVHD

Acute and chronic GVHD are graded according to CIBMTR Standard Operating Procedures. The cumulative incidence of acute grade 2- 4 GVHD, grade 3-4 GVHD within 1 year, and chronic GVHD over 1 year will be measured.

3.2.8 Serious organ toxicities by day 100

Affirmative answers to select questions on the CIBMTR forms will constitute the presence of serious organ toxicity (Table 2.6.9). The cumulative incidence by day 100 will be calculated.

3.2.9 Survival after development of acute grade 2-4 GVHD within 1 year of transplantation.

Survival will be calculated from the time of onset of grade 2 or higher acute GVHD until 1 year.

CHAPTER 4

4 SUBJECT ENROLLMENT AND EVALUATION

4.1 Enrollment Procedures

4.1.1 Approaching Subjects

Subjects may be approached for enrollment when considering allogeneic transplantation if they are expected to be age 60 years or older at the time of enrollment. Eligibility criteria will be verified, and ineligible subjects will proceed off study and no study procedures will be conducted. Eligible subjects willing to potentially participate in the trial will have a thorough discussion about the protocol with the study staff at their institution.

As this study carries low potential risk for harms, this discussion may take place by telephone to prepare subjects for the consent visit and study procedures. Telephone discussion will reduce barriers underscored by Hurria and colleagues such as distance from the center, costs of additional visits, or functional compromise.⁵⁷ This telephone discussion also will benefit subjects by improving the efficiency of the study visit by allowing the study team to prepare materials and allowing the subject to allot adequate time. Study testing and procedures will only occur after written informed consent.

Subjects will be considered enrolled once informed consent is obtained. Subjects will be registered using the EDC System Medidata Rave. Prior to initiation of the study specific activities, an authorized user at the transplant center will complete the enrollment forms in Medidata Rave.

4.1.2 Monitoring Accrual

Subject enrollment and accrual among older adults will be monitored at each participating site. The goals are to accrue a high proportion of eligible subjects at each participating center, to meet overall accrual goals and to have a diverse representative population. Centers not enrolling a high proportion of eligible subjects will be contacted to determine whether there are barriers in approaching subjects.

4.1.3 Age

We aim to have high representation of the oldest subjects, with those 70 years and older representing 20% of the enrolled study population. Present estimates suggest ~20% of subjects 60 years and older treated at BMT CTN centers are 70 years or older (unpublished CIBMTR data). In monitoring accrual, the study team will review overall protocol accrual and center specific accrual by age (60-69 and 70 and older) including potentially eligible but not accrued patients through CIBMTR data of patients undergoing allogeneic HCT. Recruitment methods may be reviewed and adjusted if needed to accommodate additional subjects 70 years or older.

4.1.4 Affiliate Centers

Affiliate centers will be encouraged to participate, with the expectation that a high proportion of subjects who are eligible will be enrolled at the site to ensure broad representation.

4.2 Study Monitoring

4.2.1 Follow-up Schedule

The follow-up schedule for study visits is outlined in Table 4.2.1. A detailed description of each of the forms and the procedures required for forms completion and submission can be found in the BMT CTN 1704 Rave CRF (Case Report Form) Completion Guide.

Table 4.2.1: Schedule for Study Visits

| Study visit | Time point | Target Day Before and After Transplant |
|-------------|------------|---|
| 1 | Baseline | 0 - 21 days prior to first day of conditioning* |
| 2 | 100 day | 100 -14/+21 days |
| 3 | 180 day | 180 ± 28 days |
| 4 | 365 day | 365 ± 28 days |

* 14 days for biomarkers (CRP, Albumin)

4.2.2 Case Report Forms

4.2.2.1 Criteria for Forms Submission

Criteria for timeliness of submission for all study forms are detailed in the CRF Completion Guide. Forms that are not entered into Medidata Rave within the specified time will be considered delinquent. A missing form will continue to be requested either until the form is entered into Medidata Rave and/or a Protocol Deviation Form is completed.

4.2.2.2 Reporting Subject Deaths

Recipient death information must be entered into Medidata Rave within 7 days of knowledge of the subject's death. If the cause of death is unknown at that time, it does not need to be recorded at that time. However, once the cause of death is determined, the Study Exit Form must be updated in Medidata Rave. Although death is unlikely to be related to study participation, immediate notification is also necessary to avoid the central study staff contacting a subject who is deceased.

4.2.2.3 CIBMTR Data Reporting

Centers participating in BMT CTN trials must register pre- and post-transplant outcomes on all consecutive hematopoietic stem cell transplants (defined as receiving the first dose of pre-transplant conditioning whether or not a graft infusion is performed) done at their institution during their time of participation to CIBMTR. Registration is done using procedures and forms of the Stem Cell Transplant Outcomes Database (SCTOD). (Note: Federal legislation requires

submission of these forms for all US allotransplant recipients.) Enrollment on BMT CTN #1704 must be indicated on the SCTOD pre-transplant registration form. Additionally, CIBMTR pre- and post-transplant Comprehensive Report Forms must be submitted for all subjects enrolled on this trial. CIBMTR forms will be submitted directly to the CIBMTR at the times specified on the Forms Submission Schedule. Subjects not undergoing HCT are not required to have their information reported to the CIBMTR.

4.2.2.4 Outcomes

Standard transplant outcomes including relapse, GVHD, toxicity and survival will be reported to the CIBMTR on post-transplant Comprehensive Report Forms per the standard CIBMTR schedule for the submission of these forms. For scheduling of study visits, a target day range has been provided in Table 4.2.1.

4.2.3 Adverse Event (AE) reporting

Reportable adverse events in this protocol are only those unexpected serious adverse events (SAEs) that are directly linked to study instruments, including study specific tests, (i.e. walk speed or grip strength), or completion of the study questionnaires. Toxicities related to transplant but unrelated to the study instruments are not considered adverse events from this study and do not require study specific reporting beyond what is routinely reported in FormsNet to the CIBMTR per standard practice. The events that are reportable will be reported through an expedited AE reporting system via Medidata Rave.

Risks of study participation include emotional distress from uncomfortable questions, fatigue, and the subject or study team being aware of a limitation from the study instruments that they would not normally be aware of. Risks of a blood draw include pain, infection and bleeding.

4.2.4 Subject Evaluations

Table 4.2.4 summarizes assessments over the course of the study.

Table 4.2.4: Study Assessments

| Study Assessments / Testing | Healthcare Team (H) or Subject Report (P) or Lab (L)* | Baseline (Pre-conditioning) | Day 100 - 14/+21 (abbreviated survey) | Day 180 +/- 28 | Day 365 +/- 28 |
|--|---|-----------------------------|---------------------------------------|----------------|----------------|
| Subject report | | | | | |
| Race/ethnicity, education, income, demographics | P | X | | | |
| Karnofsky performance status (KPS) by subject | P | X | X | X | X |
| PROMIS Physical function domain | P | X | X | X | |
| PROMIS Depression domain | P | X | X | X | X |
| PROMIS Anxiety domain | P | X | X | X | X |
| Facility admissions ³ | P | | X ⁵ | X ⁵ | X ⁵ |
| OARS IADL ¹ | P | X | X | X | X |
| Falls | P | X | X ⁵ | X ⁵ | X ⁵ |
| Frailty phenotype - Weight loss ² | P | X | X ⁵ | X ⁵ | X ⁵ |
| Frailty phenotype - Exhaustion ² | P | X | X | X | X |
| Frailty phenotype- Activity level ² | P | X | X | X | X |
| Number of medications for polypharmacy | P | X | | | |
| Healthcare team report | | | | | |
| Frailty phenotype - Walk Speed, 4 meter ² | H | X | X ⁷ | X ⁷ | X ⁷ |
| Frailty phenotype- Grip Strength ² | H | X | X | X | X |
| Montreal Cognitive Assessment (MoCA) for cognition | H | X | X ⁷ | | |
| CIBMTR Forms | H | X | X | X | X |
| Physician Prognostication Questionnaire | H ⁸ | X | | | |
| Early End of Study Questions (as needed) ⁶ | H | X | | | |
| Laboratory Testing | | | | | |
| CRP ⁴ | L | X | | | |
| Albumin ⁴ | L | X | | | |

*To be performed within 21 days prior to start of conditioning. If multiple values, enter value closest to conditioning.

- 1 OARS IADL 7 questions, omit “laundry” from Lawton IADL
- 2 Fried Frailty phenotype (5 point index). Subject report domains are weight loss, exhaustion and activity level and health care team reports walk speed and grip strength.
- 3 Overnight admission to any facility including nursing-home, subacute rehabilitation
- 4 Standard of care laboratory tests. Must be performed within 14 days prior to start of conditioning.
- 5 The time period for day 100 and day 180 questions will be the prior 3 months and at day 365 the prior 6 months.

- 6 For those who enroll but do not pursue transplantation
- 7 Assessment may be conducted remotely, as described in Appendix 6.3.3. if it is not feasible to conduct the assessment in-person.
- 8 Physician Prognostication Questionnaires completed >30 days after date of transplant will be considered missing. A protocol deviation should be submitted if the questionnaire is not sent to the provider prior to conditioning, is sent to the provider after initiation of the conditioning regimen, or if the questionnaire is not completed, but does not need to be submitted if the questionnaire is returned late by the provider (i.e., is completed by the provider after initiation of the conditioning regimen).

4.2.5 Subject-reported data capture

At the time a subject enrolls in the study, the CIBMTR Survey Research Group (SRG) is notified and then adds that subject to CIBMTR's electronic Subject Reported Outcomes (ePRO) system for data collection tracking.

Pre-transplant subject-reported data will be collected by the center electronically or on paper forms within 21 days prior to the start of conditioning. If conditioning is delayed, the subject-reported surveys should be repeated so they are within 21 days of start of conditioning. Electronically collected pre-transplant instruments will be directly entered in the ePRO system via unique links. The center will securely email or fax pre-transplant instruments completed on paper to the SRG to enter into their electronic ePRO system. Along with the pre-transplant instruments, the center will complete the required forms in FormsNet prior to the 100 day visit so that the SRG can reach the subject for all post-transplant time points.

The SRG will administer the 100 day, 180 day and 365 day instruments online, or on paper if requested by the subject. The SRG will first confirm each subject's clinical status with the transplant center because reporting of deaths may lag. The SRG will then contact the subject via email, phone or mail to collect the subject reported information online or on paper. The SRG will follow-up with non-responders to minimize missing forms. Data will continue to be collected even if the subject has relapsed disease and/or undergone treatment for relapse to the extent feasible.

- 100 days -14/+21 days
- 180 days +/- 28 days
- 365 days +/- 28 days

At the conclusion of each subject reported data collection, subjects will be reminded of the next date of contact. The SRG will notify the transplant center if a subject's contact information has changed or if they find through follow-up that the subject has died, and centers will be required to update and enter Rave forms accordingly.

4.2.6 Quality Control:

This protocol includes tools that must be administered by a health care team member (e.g., research coordinator, nurse etc.) such as walk speed, grip strength and cognition. Standardized administration of these tools across sites will reduce measurement error and improve generalizability of results. Therefore, site staff administering these tests will be required to attend mandatory training. Video training will also be made available to view. A log of trained users

will be maintained by the protocol team. Specifically, regarding the MoCA assessment, each site should have a “super-user” who has completed online certification and can also train other staff to perform the testing.

CHAPTER 5

